1. PROTOCOL SUMMARY

1.1. Synopsis

Protocol Title: A Three-Part FTIH Study to Evaluate Safety, Tolerability, Pharmacokinetics and Pharmacodynamics of Single and Repeat Oral Doses of GSK3439171A, in a Randomized, Double-Blind (sponsor unblinded), Placebo-Controlled, Dose Escalation study and to Evaluate the Effect of Food on a Single Oral Dose of GSK3439171A in Healthy Adult Participants

Short Title: FTIH Study to evaluate the safety, pharmacokinetics, and pharmacodynamics of single and repeat doses of GSK3439171A in healthy participants; food effect

Rationale: The FTIH study with GSK3439171A will evaluate the safety of GSK3439171A in healthy participants in order to avoid confounding factors due to the disease or concomitant drugs in patients. The study design is based on pre-clinical findings for GSK3439171A, contributing to the frequency, type and duration of safety assessment and monitoring during treatment periods in each cohort.

The single dose assessments in Part A will be conducted to determine safety, tolerability, pharmacokinetics (PK), and pharmacodynamics (PD) of the study intervention in individuals before progressing to doses explored further in other parts of the study and will allow for any adjustments needed based on emerging safety, tolerability, and PK information. Part A will also serve to identify a dose for use in examining the effect of food on GSK3439171A exposure in Part C.

In Part B, a single dose safety, tolerability and PK will be collected followed by progression of these participants to the repeat dose portion of the study. The up to 14-day dosing was chosen as it is thought to provide sufficient safety and tolerability data to bridge to longer duration studies. The dosing period can be adjusted depending on PK and PD data collected in Part A of the study. Part B will involve more detailed PK/PD/metabolite assessments to better understand the impact of GSK3439171A on target engagement and metabolism in humans. In addition, based on the PK obtained in Part A, an additional cohort will be enrolled to study higher exposures of GSK3439171A for a shorter duration of time.

Objectives and Endpoints:

Objective	Endpoint
Primary	

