Participants will report to the Clinical Research Unit on Day -2 and will remain in the unit for the duration of Part B. Participants will randomly be assigned to receive a single dose (or a BID dose depending on data obtained in Part A) of GSK3439171A or placebo (approximately 9 study intervention: 3 placebo). Plasma and urine PK, PD, and biomarker samples (including a pre-dose muscle biopsy) will be collected for up to 72 hr after initial dosing. After completion of assessments at 72 hr (Day 4), participants will begin a repeat dosing regimen consisting of one dose (or a BID dose depending on data obtained in Part A) per day for up to 14 days. This time period is based on a predicted half-life of GSK3439171A of 6.1 hours (with a range of 4-22 hours) calculated from preclinical data and is designed to allow GSK3439171A to reach steady state during the dosing period. The actual repeat dose duration can be altered based on PK data in Part A of the study. For example, if the predicted half-life is confirmed from Part A of the study then the duration of dosing in Part B will be much shorter to achieve steady-state than planned currently. Dosing duration in Part B and follow-up will be shortened appropriately based on emerging PK data from Part A. Participants will be discharged on the morning of Day 13 (3 days post last dose during the 7 day repeat dose period) or Day 20 (3 days post-last dose during the 14 day repeat dose period) following completion of study assessments, including a post-dose muscle biopsy. Safety, tolerability and PK data review for a minimum of 6 participants receiving active treatment will be carried out upon completion of assessments on Day 13 or 20 (72 hours post-last dose) before initiation of dosing in the next cohort. The dose of GSK3439171A may be adjusted (lower or higher) based on data from Part A and for cohorts going forward based upon the safety, tolerability, PK, and preliminary PD data from the previous cohort.

All participants will return to the clinical unit for a follow-up visit approximately 14 days following the administration of the last dose of study medication.

Part C: Food Effect

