6.3. Measures to Minimize Bias: Randomization and Blinding

6.3.1. Randomization

Study using Pre-Coded Randomization provided to site	Before treatment begins at the beginning of each part of the study, participants will be assigned a unique number (randomization number) in ascending numerical order at the study site. The randomization number encodes the participant's assignment to the respective arms of the study, according to the randomization schedule generated prior to the study by the Clinical Statistics Department at GSK. Each participant will be dispensed blinded study intervention, labeled with his/her unique randomization number throughout the study.
---	--

In Part A, approximately 9 participants in each cohort will be randomized to one of 3 treatment sequences (AAP, APA & PAA, where A represents an active dose of GSK3439171 and P represents placebo). Within each period, allocation of active (A) to placebo (P) treatment will be 2:1. Within a cohort, an increasing dose of GSK3439171A will be administered in each period as illustrated in the table below. Planned doses are provided in Section 6.6. At each dose level, sentinel dosing will be employed, such that one subject is dosed with placebo and another with active dose of GSK3439171A and followed for 48 hr prior to the rest of the subjects receiving their randomized treatment.

Cohort	Sequence	Period 1	Period 2	Period 3
Cohort 1	AAP	D1	D2	Placebo
	APA	D1	Placebo	D3
	PAA	Placebo	D2	D3
Cohort 2	AAP	D4	D5	Placebo
	APA	D4	Placebo	D6
	PAA	Placebo	D5	D6
Cohort 3	AAP	D7	D8	Placebo
	APA	D7	Placebo	D9
	PAA	Placebo	D8	D9

In each cohort of Part B, approximately 12 participants will be randomized to receive either GSK3439171A or placebo in a parallel design using a 3:1 allocation ratio. Participants will receive a single dose followed by a 72 hr assessment period and then will receive daily repeat doses until the end of the study.

Dose Cohort	Regimen
B1	R1 mg GSK3439171A or placebo QD or BID
B2 ¹	R2 mg GSK3439171A or placebo QD or BID
B3 ¹	R3 mg GSK3439171A or placebo QD or BID

1. Dose levels for Cohorts will be determined based on real-time analysis of the safety, tolerability, PK, and preliminary PD data from Part A and therefore may be adjusted from predicted dose levels listed.

QD – Once daily

BID- Twice daily

Regimen	Period 1	Period 2
X	GSK3439171A ¹ administered in the fasted state	GSK3439171A ¹ administered after a high fat meal

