2.2. Study Objective(s) and Endpoint(s)

[figure not shown]
Objectives	Endpoints
Primary Objectives	Primary Endpoints
To assess the safety and tolerability of GSK3439171A following single and repeat doses in healthy participants	Adverse events (AE), Serious Adverse Events (SAE), clinical laboratory values, vital signs, and electrocardiograms (ECG)
To characterize the PK of GSK3439171A, following single and repeat doses in healthy participants	Derived PK parameters for GSK3439171A including area under the plasma drug concentration versus time curve (AUC(0-t), AUC(0-inf), maximum observed plasma drug concentration (Cmax), time to maximum observed plasma drug concentration (tmax), and apparent terminal half-life (t1/2) as appropriate
Secondary Objectives	Secondary Endpoints
To assess the effect of food on the PK of GSK3439171A following an oral dose in healthy participants	Derived PK parameters for GSK3439171A including area under the plasma drug concentration versus time curve (AUC(0-t), AUC(0-inf), maximum observed plasma drug concentration (Cmax), time to maximum observed plasma drug concentration (tmax), and apparent terminal half-life (t1/2) as appropriate
To assess preliminary dose proportionality of GSK3439171A following single and repeat oral doses, as data permit	AUC(0-t), AUC(0-inf), and Cmax following single dose and AUC(0-τ) and Cmax following repeat dose for the assessment of dose proportionality
To examine the extent of accumulation and achievement of steady-state following repeat oral doses of GSK3439171A, as data permits	
 Determine observed accumulation based on AUC(Ro) and Cmax (RCmax) and determine the steady-state ratio (Rss) Trough plasma concentrations at the end of the dosing interval (Cτ) collected pre-dose for repeat doses 12, 13 and 14* to assess the achievement of steady-state of GSK3439171A
Exploratory Objectives	Exploratory Endpoints
To evaluate the PD properties of GSK3439171A	Levels of mediators on prostaglandin and/or inflammatory metabolic pathways such as, but not limited to, PGD2, and PGE2.
To assess the effect of GSK3439171A on QTc in healthy adult volunteers	Holter monitor data collection and storage for evaluation of the correlation between plasma levels of GSK3439171A and changes in the QTc interval in the future, if appropriate
To evaluate additional biomarkers of GSK3439171A target	Levels of change in novel biomarkers in blood, muscle, or urine, such as, but not limited to, urine

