Dosing	
 • Part A: Each participant will participate in 3 dosing periods and will receive 2 doses of GSK3439171A and 1 dose of placebo in a randomized fashion. There will be an approximately 7 day (or 5 half-lives, whichever is longer) washout period between dosing in each session. Each active dose level will be administered initially to a smaller group of participants (1 on active and 1 on placebo) and will be followed clinically for 48 hr (or 5 half-lives, whichever is longer) to allow for adequate observation of safety. If no acute safety issues are observed in this smaller group of sentinel participants, then the remaining participants (approximately 5 participants on active and 2 participants on placebo) will receive the dose. • Part B: In each cohort of Part B of the study, approximately twelve participants will be randomized to either one dose level of GSK3439171A or placebo according to a randomization schedule prepared prior to the start of the study. The study will be conducted sequentially starting with Dose 1 Cohort B1. Participants will receive a single dose followed by a 48 hr assessment period and then will receive daily repeat doses until the end of the study. • Part C: In this crossover design, approximately 12 participants will take part in two periods with dosing in each period separated by approximately 7 days (or 5 half-lives of the study intervention, whichever is longer). In each study session, participants will be admitted to the clinical unit and receive a single dose of GSK3439171A either in the fasted state or after a high fat meal.
Time & Events	
 • Refer to Appendix 2: Schedule of Activities

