13.4. Appendix 4: Study Phases and Treatment Emergent Adverse Events

13.4.1. Study Phases

Assessments and events will be classified according to the time of occurrence relative to study treatment

Study Phase	Definition
Pre-Treatment	Date ≤ Study Treatment Start Date
On-Treatment	Study Treatment Start Date < Date ≤ Study Treatment Stop Date + 3 days
Post-Treatment	Date > Study Treatment Stop Date + 3 days

Note: Estimated half-life of GSK3439171 is approx. 13 hours. The maximum of (5 half-lives ~ 65 hours ~ 3days) and after the Study Treatment End Date, lag time have been considered to be 3 days to define the end of treatment phase.

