13.12.5. Safety Tables

- The requirements for each display (i.e. IDSL, ICH, FDAAA etc) specified in the programming notes may be retained, all other red reference notes should be deleted.
- Select appropriate standard based on study design (i.e. parallel vs cross-over), when applicable.
- Suggested IDSL shells are noted in the third column, but other IDSL shells may be used, as appropriate

CONFIDENTIAL

209275

- The ADaM datasets for the Core Study Population/Safety displays can be found in the IDSL Library under Reference → Statistical Displays
→ ADaM Datasets for Core RAP Displays

Safety: Tables					
No.	Population	IDSL / Example Shell	Title	Programming Notes	Deliverable [Priority]
Adverse Events (AEs)					
3.1.	Safety	CP_AE1x	Summary of All Adverse Events by System Organ Class and Preferred Term - Part A		SAC
3.2.	Safety	CP_AE1p	Summary of All Adverse Events by System Organ Class and Preferred Term - Part B		SAC
3.3.	Safety	CP_AE1p	Summary of All Adverse Events by System Organ Class and Preferred Term by Study Phase - Part B		SAC
3.4.	Safety	CP_AE1x	Summary of All Adverse Events by System Organ Class and Preferred Term - Part C		SAC
3.5.	Safety	AE5B	Summary of All Adverse Events by Maximum Grade by System Organ Class and Preferred Term – Part A		SAC
3.6.	Safety	AE5B	Summary of All Adverse Events by Maximum Grade by System Organ Class and Preferred Term – Part B		SAC
3.7.	Safety	AE5B	Summary of All Adverse Events by Maximum Grade by System Organ Class and Preferred Term – Part C		SAC
3.8.	Safety	CP_AE1x	Summary All Drug-Related Adverse Events by System Organ Class and Preferred Term- Part A		SAC
3.9.	Safety	CP_AE1p	Summary All Drug-Related Adverse Events by System Organ Class and Preferred Term - Part B	As 3.1 notes.	SAC

Safety: Tables					
No.	Population	IDSL / Example Shell	Title	Programming Notes	Deliverable [Priority]
3.10.	Safety	CP_AE1x	Summary All Drug-Related Adverse Events by System Organ Class and Preferred Term - Part C	As 3.1 notes.	SAC
3.11.	Safety	AE15	Summary of Common (>=10%) Non-serious Adverse Events by System Organ Class and Preferred Term (Number of Participant and Occurrences) – Part A	
FDAAA, EudraCT Disclosure display
 
Common' to be defined by study/project team. For studies with very few events/participants, listing is sufficient: discuss this option with your disclosure representative.
	SAC

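### SAP 13.4.1 gives the Part B single-dose stage no phase of its own, so Table 3.3 as specified does not separate single-dose from repeat-dose adverse events

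*SAP*

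**What the plan says.** SAP 13.4.1 defines three study phases for the whole study. Pre-Treatment is "Date ≤ Study Treatment Start Date", On-Treatment is "Study Treatment Start Date < Date ≤ Study Treatment Stop Date + 3 days", and Post-Treatment is everything later. A note sets the three-day lag at five half-lives of about 13 hours.

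Part B has two dosing stages. The protocol synopsis states: "In Part B, a single dose safety, tolerability and PK will be collected followed by progression of these participants to the repeat dose portion". Protocol 4.1 places the change at Day 4: "After completion of assessments at 72 hr (Day 4), participants will begin a repeat dosing regimen". Protocol 6.3.1 agrees: "Participants will receive a single dose followed by a 72 hr assessment period and then will receive daily repeat doses". SAP 2.3 gives a different interval: "Participants will receive a single dose followed by a 48 hr assessment period and then will receive daily repeat doses". The first primary objective, as restated in SAP 2.2, covers both stages: "To assess the safety and tolerability of GSK3439171A following single and repeat doses in healthy participants".

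The only adverse event table by phase is Table 3.3 in SAP 13.12.5, "Summary of All Adverse Events by System Organ Class and Preferred Term by Study Phase - Part B". Its programming note is blank, so nothing there overrides 13.4.1. The other Part B adverse event summaries (Tables 3.2, 3.6, 3.9, 3.12 and 3.15) are not by phase. Listing 42 lists every Part B event.

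**The concern.** Part B can show whether an event arises after one dose or only once dosing continues, in the same participants and against concurrent placebo. Protocol 6.6.2 expects accumulation to put the highest exposure on the last day of dosing, so early and late onset carry different information. The SAP keeps this distinction for pharmacokinetics: its Table 2 derives parameters after dose 1 and at steady state. Safety, the other primary objective, gets no equivalent summary. Because the phases hang on one start date and one stop date, nothing marks the move to repeat dosing, and the one table that could show the contrast does not.

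**Working it through.** **Inputs**

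- Phase rules and half-life: SAP 13.4.1.
- First dose on Day 1, repeat dosing from Day 4: Protocol 4.1 and 6.3.1.
- Last dose: Protocol 4.1 puts discharge on Day 20 (14-day regimen) or Day 13 (7-day regimen), each three days after the last dose. So the stop date is 20 − 3 = Day 17 or 13 − 3 = Day 10. Check: Days 4-17 are 14 dosing days and Days 4-10 are 7.
- Cohorts: SAP 5.1 and the footnote to SAP Table 3 make cohort 3 (40 mg) the 7-day cohort; 5 and 11 mg are the 14-day cohorts.

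**1. The plan's own figure.** 5 × 13 h = 65 h; 65 / 24 = 2.71 days, rounded up to 3. This reproduces the SAP's lag.

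**2. Apply 13.4.1 to each study day (start = Day 1)**

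| Regimen | Pre-Treatment (day ≤ 1) | On-Treatment (1 < day ≤ stop + 3) | Single-dose days in On-Treatment | Repeat-dose days in On-Treatment |
|---|---|---|---|---|
| 14-day | Day 1 | Days 2-20 (19 days) | Days 2-3 (2) | Days 4-20 (17) |
| 7-day | Day 1 | Days 2-13 (12 days) | Days 2-3 (2) | Days 4-13 (10) |

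The 72 h single-dose stage (Days 1-3) is divided between two phases and isolated in neither.

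**3. Share of the pooled phase.** 2/19 = 0.105, about 11% (14-day). 2/12 = 0.167, about 17% (7-day). These are shares of days, not of events; the documents give no event rate.

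**4. Day 1 against the imputation rule.** Under 13.4.1 an event dated on the start date is Pre-Treatment. Under SAP 13.7.2.1 an event with a missing start day that is moved to the treatment start date counts as On-Treatment and cites the same appendix. The same date gets two phases. Protocol 8.3.1 collects adverse events only once treatment has started (serious events related to study participation are recorded from consent). Apart from those, the Part B Pre-Treatment phase would hold essentially only post-dose Day 1 events.

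**5. Can the stages be separated?** On the protocol's schedule, yes. The SAP's 65 h lag after the Day 1 dose ends before the Day 4 dose at 72 h. On the SAP's 48 h figure, the lag would run 65 − 48 = 17 h past the end of the assessment period. The two figures therefore need reconciling, and a cut at the dose actually given does not depend on either.

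**The case against.** The strongest reply is that Table 3.3 already means single versus repeat dose. It is planned for Part B alone, the one part with two dosing stages. Protocol 9.4 uses the term study phase for single and repeat dosing in its pharmacokinetic headings. A before/during/after layout also adds little when events are collected only from the start of treatment. That may have been the intent. But the SAP defines study phase once, in 13.4.1, and differently, and Table 3.3 has no note to the contrary. A programmer who follows the SAP produces the three-phase table.

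The second reply is that no information is lost. Safety is descriptive, and individual data are reviewed by plan. With about 9 active and 3 placebo participants per cohort, Listing 42 can be sorted by onset. This stands, and it limits the severity.

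The third is that Part A summarises single-dose events at 5, 10, 30, 60, 120 and 180 mg. This stands in part: those are different participants, and neither 11 nor 40 mg is among the doses.

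The fourth is that SAP 5.1 gives cohort 3 its own placebo group, so 40 mg has a comparator on the same schedule. This also stands. The different mix of stages affects comparisons across doses, not that contrast with placebo.

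**Conclusion.** The point holds as a minor one. As specified, Table 3.3 does not isolate the Part B single-dose stage. Day 1 post-dose events are labelled Pre-Treatment, and Days 2-3 are pooled with repeat dosing, at 2 of 19 days (14-day cohorts) and 2 of 12 days (7-day cohort). Separation is then possible only by hand from Listing 42. This rests on the protocol's Day 4 start of repeat dosing, last doses on Days 17 and 10, and a date-level reading of 13.4.1.

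Three stronger readings are tempting and are not supported:

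- A reader might infer that the whole 72 h falls into On-Treatment, making 3 of 20 or 3 of 13 days. The strict inequality in 13.4.1 excludes Day 1.
- A reader might infer that the single-dose stage is the only window of equal length in every Part B cohort. Post-Treatment is also about equal, because it runs from three days after the last dose to a follow-up visit about 14 days after it.
- A reader might infer that single-dose safety in Part B goes unreported. It is listed; what is missing is a summary.

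**What to change.** In SAP 13.4.1:

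- **Pre-Treatment:** onset before the first dose, by date and time. An event on the first-dose date with missing time counts as after dosing. This also removes the conflict with 13.7.2.1. In Parts A and C, On-Treatment should then begin at the first dose, so that Day 1 events are not left without a phase.
- **Part B, in place of On-Treatment:** *Single dose*, onset from the first dose to before the first repeat dose actually given (or to last dose + 3 days if none is given); and *Repeat dose*, onset from the first repeat dose to last dose + 3 days. State the same missing-time convention for the date of the first repeat dose.
- **Post-Treatment:** unchanged.

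Present Table 3.3 by these phases and by dose, placebo included, and say so in its programming note. Anchor on the dose actually given, because the notes to the Part B schedule in Protocol 1.3 allow the start of repeat dosing to move. Reconcile the 48 h in SAP 2.3 with the 72 h in Protocol 4.1 and 6.3.1.

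The cost is a few lines of SAP text and one derived variable, with no new data and no new table. Dose dates and times are recorded under Protocol 6.4. The documents do not say whether adverse event onset times are collected; if they are not, the missing-time conventions settle the boundary days.

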8.3.1. Time Period and Frequency for Collecting AE and SAE Information

- All SAEs will be collected from the start of intervention until the follow-up visit at the time points specified in the SoA (Section 1.3). However, any SAEs assessed as related to study participation (e.g., study intervention, protocol-mandated procedures, invasive tests, or change in existing therapy) or related to a GSK product will be recorded from the time a participant consents to participate in the study.
- All AEs will be collected from the start of intervention until the follow-up visit at the time points specified in the SoA (Section 1.3).
- Medical occurrences that begin before the start of study intervention but after obtaining informed consent will be recorded on the Medical History/Current Medical Conditions section of the CRF not the AE section.
- All SAEs will be recorded and reported to the sponsor or designee immediately and under no circumstance should this exceed 24 hours, as indicated in [Appendix 3](#). The investigator will submit any updated SAE data to the sponsor within 24 hours of it being available.
- Investigators are not obligated to actively seek AEs or SAEs after the conclusion of the study participation. However, if the investigator learns of any SAE, including a death, at any time after a participant has been discharged from the study, and he/she considers the event to be reasonably related to the study intervention or study participation, the investigator must promptly notify the sponsor.

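### Part B adverse-event tables set 40 mg (about 24 days of observation) beside 5 and 11 mg (about 31 days) with no common window or rate, so a modest dose-related increase could look flat

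*SAP*

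**What the plan says.** Protocol 4.1 gives Part B participants a single dose on Day 1. Then: "After completion of assessments at 72 hr (Day 4), participants will begin a repeat dosing regimen". The shorter schedule ends with discharge on "Day 13 (3 days post last dose during the 7 day repeat dose period"). The longer schedule ends with discharge on "Day 20 (3 days post-last dose during the 14 day repeat dose period"). Under both, everyone returns for a "follow-up visit approximately 14 days following the administration of the last dose of study medication". Protocol 8.3.1 sets the collection window: "All AEs will be collected from the start of intervention until the follow-up visit at the time points specified in the SoA".

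SAP 5.1 displays the three Part B doses as 5, 11 and 40 mg. It lists a cohort 3 placebo separately from the other Part B placebo. The footnote to SAP Table 3 (section 8.2.1.2) identifies cohort 3 as the cohort with the reduced treatment period.

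SAP 13.4.1 defines on-treatment as "Study Treatment Start Date < Date ≤ Study Treatment Stop Date + 3 days". The lag rests on the note "Estimated half-life of GSK3439171 is approx. 13 hours", with five half-lives rounded to 3 days.

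SAP 13.12.5 lists the Part B AE tables: 3.2 (all AEs), 3.3 ("Summary of All Adverse Events by System Organ Class and Preferred Term by Study Phase - Part B"), 3.6 (maximum grade), 3.9 (drug-related) and 3.12 (common non-serious). SAP 13.6.1 adds a pooled active column to the Part B safety summaries. SAP 13.5.2 specifies N, n, frequency and percentage for categorical data. None of these places mentions a common observation window, a rate per unit of time, or a note on differing follow-up.

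**The concern.** The top dose has the shortest dosing period, and therefore the shortest time in which an AE can be counted. A percentage of participants with at least one AE rises with observation time even when the drug does nothing. Columns of unequal length placed side by side therefore lean toward fewer events at 40 mg.

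Repeat-dose safety and tolerability is a primary objective and is assessed descriptively. Protocol 9.2 says Part B should support dose selection for later studies, so readers will look along the dose columns for a trend. The lean runs against seeing one.

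Elsewhere the SAP allows for the two schedules. It substitutes Day 10 for Day 17 in the accumulation and steady-state ratios, uses separate trough days, and panels the PD plots by day. The AE tables have no equivalent.

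**Working it through.** **1. Reproduce the plan's own days.** Last dose = Day 4 + n − 1, for n repeat-dosing days.

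- n = 14: Day 17; plus 3 = Day 20.
- n = 7: Day 10; plus 3 = Day 13.

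Both match the discharge days in Protocol 4.1. Counting in-house days from Day -2 with no Day 0 gives 2 + 20 = 22 and 2 + 13 = 15, which matches the 15-22 days in the synopsis. The lag is 5 × 13 h = 65 h = 2.7 days, taken as 3.

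**2. Observation windows.**

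| | 5 and 11 mg | 40 mg | Ratio |
|---|---|---|---|
| First dose to follow-up (last dose + 14, ±1) | Days 1-31: 31 days | Days 1-24: 24 days | 24/31 = 0.77 |
| On treatment (strictly after start date, to stop date + 3) | Days 2-20: 19 dates | Days 2-13: 12 dates | 12/19 = 0.63 |

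The pooled active column, at 9 per cohort, averages (18 × 31 + 9 × 24)/27 = 774/27 = 28.7 days.

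**3. Expected percentages with no drug effect.** The documents give no AE rate, so a constant background rate r of 1%, 2% or 3% per day is assumed. Incidence = 1 − exp(−r × T).

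| r per day | T = 31 | T = 24 | Ratio | Gap of 9 | T = 19 | T = 12 | Ratio | Gap of 9 |
|---|---|---|---|---|---|---|---|---|
| 1% | 26.7% | 21.3% | 0.80 | 0.5 | 17.3% | 11.3% | 0.65 | 0.5 |
| 2% | 46.2% | 38.1% | 0.83 | 0.7 | 31.6% | 21.3% | 0.68 | 0.9 |
| 3% | 60.5% | 51.3% | 0.85 | 0.8 | 43.5% | 30.2% | 0.70 | 1.2 |

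**4. What could be hidden.** Equal percentages would appear if the true daily rate at 40 mg were 31/24 = 1.29 times the lower-dose rate (all AEs) or 19/12 = 1.58 times (on treatment).

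**5. How often the lean would show.** Take an assumed risk between 10% and 90% in the longer window, a constant rate, and independent binomial counts with 9 per dose. The chance that 40 mg shows fewer affected participants than one lower-dose column is 38-57% for all AEs and 42-69% on treatment. The chance that it shows more is 21-29% and 13-23%. The rest are ties.

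**6. After a common window.** With no drug effect, and with equal observation, dosing days and procedures, the expected ratio is 1.00, without needing a constant rate.

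**The case against.** The strongest reply is that the plan does not set out to compare doses. Protocol 9.4.1 and SAP section 7 describe comparison with placebo and review of individual data, and SAP 5.1 lists dose-versus-placebo displays. The separate cohort 3 placebo column gives 40 mg a comparator on the same 7-day schedule. This stands: a reader might infer that the 40 mg versus placebo contrast is distorted, and it is not, provided the cohort 3 placebo is used. Its limit is size, at about 3 participants. It does not help the reading across doses, and the pooled column at 28.7 days matches neither placebo column.

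A reader might also infer that an inert drug will show fewer AEs at 40 mg. The documents do not support that. The deficit holds in expectation, under a roughly constant rate, and with 9 per dose the observed order can go either way. Events tied to fixed procedures, such as biopsies and serial blood sampling, need not grow with days.

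Nor is the on-treatment definition at fault. It applies one rule to every cohort; the inequality comes from the deliberate 7-day and 14-day schedules. Of the five tables, only 3.3 is titled by study phase, and the 31 versus 24 days would remain without the phase rule.

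The imbalance is also visible: Table 1.33 summarises exposure, and Listings 39 and 42 give exposure and every AE for Part B. That discloses the difference but does not correct the percentages. Finally, escalation relies on in-stream reviews and the stopping rules work within the current dose group, so the documents do not tie those decisions to these tables.

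**Conclusion.** The point holds for the dose-to-dose reading and the pooled active column. The windows (about 31 versus 24 days, and 19 versus 12 dates) follow directly from the documents, and no adjustment is planned. With no drug effect and a roughly constant rate of 1-3% per day, the 40 mg percentage is expected to be 0.80-0.85 of the lower-dose percentage overall and 0.65-0.70 on treatment. In participants the gap is about 0.5-0.8 of 9 overall and 0.5-1.2 of 9 on treatment.

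These sizes rest on an assumed rate and its constancy; the direction needs only that some AEs arise in the extra days. The lean is small beside the sampling noise at 9 per dose, but it is systematic, it falls on the highest dose, and it could make a modest increase look flat. It is worth correcting because the correction uses data already collected.

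**What to change.** In SAP 13.12.5:

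- Keep all full-period Part B AE tables.
- Add person-days of observation and events per 100 person-days for each column to Tables 3.2 and 3.3. These rates still assume a roughly constant rate over time.
- Add a version of Tables 3.2, 3.6, 3.9 and 3.12 limited to AEs with onset from first dose to before the first dose on Day 10, and use it when comparing doses. If only onset dates are recorded, the last date included is Day 9.

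The cut belongs before the Day 10 dose. Up to then all cohorts share the same planned dosing days (Day 1 and Days 4-9). Cohort 3's post-dose biopsy and full last-dose PK profile start on Day 10; in the 14-day cohorts the last-dose profile starts on Day 17. A cut at the end of Day 10 would load procedure-related events onto 40 mg.

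The cost is SAP wording and a few re-filtered tables from existing data, with no change to conduct. The drawback is that later events, including 40 mg events on Days 10-13, appear only in the full-period tables.
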